11.0 Reporting Requirements

An adverse event is the appearance or worsening of any undesirable sign, symptom, or medical condition occurring after starting the study drug even if the event is not considered to be related to study drug. Medical conditions/diseases present before starting study drug are only considered adverse events if they worsen after starting study drug. Abnormal laboratory values or test results constitute adverse events only if they induce clinical signs or symptoms, are considered clinically significant, or require therapy.

The investigator (or physician designee) is responsible for verifying and providing source documentation for all adverse events and assigning the attribution for all adverse events for subjects enrolled.

Adverse event reporting will be as per the NCI criteria and the MDACC Leukemia Specific Adverse Event Recording and Reporting Guidelines (Appendix C).

The descriptions and grading scales found in the revised NCI Common Terminology Criteria for Adverse Events (CTCAE) version 4.0 will be utilized for adverse event reporting. (<http://ctep.cancer.gov/reporting/ctc.html>).

Protocol specific data will be entered into PDMS/CORe. PDMS/CORe will be used as the electronic case report form for this protocol. All AEs, regardless of expectedness will be collected and recorded on the Adverse Event Record and scanned into the patient's medical record. However, only unexpected AEs will be recorded in the Case Report Form (CRF). The Principal Investigator will sign and date the PDMS Case Report Form toxicity pages per each patient at the completion of each course. Following signature, the Case Report Form will be used as source documentation for the adverse events for attribution.

Serious Adverse Event Reporting (SAE) for M. D. Anderson-sponsored IND Protocols

An adverse event or suspected adverse reaction is considered "serious" if, in the view of either the investigator or the sponsor, it results in any of the following outcomes:

- Death
- A life-threatening adverse drug experience – any adverse experience that places the patient, in the view of the initial reporter, at immediate risk of death from the adverse experience as it occurred. It does not include an adverse experience that, had it occurred in a more severe form, might have caused death.
- Inpatient hospitalization or prolongation of existing hospitalization

- A persistent or significant incapacity or substantial disruption of the ability to conduct normal life functions.
- A congenital anomaly/birth defect.

Important medical events that may not result in death, be life-threatening, or require hospitalization may be considered a serious adverse drug experience when, based upon appropriate medical judgment, they may jeopardize the patient or subject and may require medical or surgical intervention to prevent one of the outcomes listed in this definition. Examples of such medical events include allergic bronchospasm requiring intensive treatment in an emergency room or at home, blood dyscrasias or convulsions that do not result in inpatient hospitalization, or the development of drug dependency or drug abuse (21 CFR 312.32).

- Important medical events as defined above, may also be considered serious adverse events. Any important medical event can and should be reported as an SAE if deemed appropriate by the Principal Investigator or the IND Sponsor, IND Office.
- All events occurring during the conduct of a protocol and meeting the definition of a SAE must be reported to the IRB in accordance with the timeframes and procedures outlined in "The University of Texas M. D. Anderson Cancer Center Institutional Review Board Policy for Investigators on Reporting Unanticipated Adverse Events for Drugs and Devices". Unless stated otherwise in the protocol, all SAEs, expected or unexpected, must be reported to the IND Office, regardless of attribution (within 5 working days of knowledge of the event).
- **All life-threatening or fatal events**, that are unexpected, and related to the study drug, must have a written report submitted within **24 hours** (next working day) of knowledge of the event to the Safety Project Manager in the IND Office.
- Unless otherwise noted, the electronic SAE application (eSAE) will be utilized for safety reporting to the IND Office and MDACC IRB.
- Serious adverse events will be captured from the time of the first protocol-specific intervention, until 30 days after the last dose of drug, unless the participant withdraws consent. Serious adverse events must be followed until clinical recovery is complete and laboratory tests have returned to baseline, progression of the event has stabilized, or there has been acceptable resolution of the event.
- Additionally, any serious adverse events that occur after the 30 day time period that are related to the study treatment must be reported to the IND Office. This may include the development of a secondary malignancy.

Reporting to FDA:

- Serious adverse events will be forwarded to FDA by the IND Sponsor (Safety Project Manager IND Office) according to 21 CFR 312.32.

It is the responsibility of the PI and the research teams to ensure serious adverse events are reported according to the Code of Federal Regulations, Good Clinical Practices, the protocol guidelines, the sponsor's guidelines, and Institutional Review Board policy.

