Data from all subjects who receive any study drug will be included in the safety analyses. Subjects who entered the study but did not take any of the study drug and had this confirmed will not be evaluated for safety. The severity of the toxicities will be graded according to the NCI CTCAE v4.0 whenever possible. We will follow standard reporting guidelines for adverse events. Safety data will be summarized by AE category, severity and frequency. The proportion of patients with AEs will be estimated.

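### The electronic CRF takes only unexpected adverse events, so the study database as specified lacks the non-serious expected events that the planned safety summaries cover

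*Combined protocol and SAP*

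**What the plan says.** Two sections of the protocol carry the number 11.0, and both matter here.

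Section 11.0 Reporting Requirements sets out where AE data go:

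- The database: "Protocol specific data will be entered into PDMS/CORe. PDMS/CORe will be used as the electronic case report form for this protocol".
- The full AE record: "All AEs, regardless of expectedness will be collected and recorded on the Adverse Event Record and scanned into" the patient's chart.
- The limit on database entry: "However, only unexpected AEs will be recorded in the Case Report Form (CRF").
- Serious events: "all SAEs, expected or unexpected, must be reported to the IND Office, regardless of attribution", and, on the system used, "Unless otherwise noted, the electronic SAE application (eSAE) will be utilized for safety reporting to the IND Office and MDACC IRB".
- The governing guideline: "Adverse event reporting will be as per the NCI criteria and the MDACC Leukemia Specific Adverse Event Recording and Reporting Guidelines (Appendix C"). That appendix is not in the text supplied.

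The same section makes the investigator responsible for attributing every AE, and makes the signed CRF the source document for attribution.

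Section 11.0 Statistical Considerations sets out the analysis. On the population: "Data from all subjects who receive any study drug will be included in the safety analyses". On the outputs: "Safety data will be summarized by AE category, severity and frequency. The proportion of patients with AEs will be estimated". Its Analysis Plan names tolerability as a secondary endpoint, and objective 1.2.2 is to describe the safety, tolerability and AE profile of the two agents.

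**The concern.** The recording rule is narrower than the analysis it has to feed. The planned summaries are not restricted by expectedness, but the database is. Whatever is classed as expected and is not serious would be missing from any table built from the CRF, even with the serious-event reports added.

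The events left out are probably those that a tolerability endpoint should describe. Section 3.1.7 reports transient nausea and vomiting with both oral and intravenous levocarnitine, and other mild gastrointestinal complaints with long-term oral use. Treating these as expected is an inference, because the supplied text does not define the term.

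At stake are the proportion of patients with AEs and the category, severity and frequency tables, all of which could be too low. Attribution is affected too: an expected event that never enters the CRF has no attribution in the document designated as its source. The primary endpoint, stopping rule and error rates are not affected.

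**Working it through.** The plan gives no figure to reproduce on this point. The check sets the recording rules against the planned outputs and then works out the effect per patient.

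**Step 1. Where each kind of AE is recorded** (section 11.0 Reporting Requirements)

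| Kind of AE | Adverse Event Record (scanned to chart) | CRF (PDMS/CORe) | eSAE |
|---|---|---|---|
| Unexpected, serious | yes | yes | yes |
| Unexpected, non-serious | yes | yes | no |
| Expected, serious | yes | no | yes |
| Expected, non-serious | yes | **no** | **no** |

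Only the last row is missing from both electronic sources. Nothing in the supplied text has the scanned record abstracted, coded or entered for analysis.

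**Step 2. What the analysis needs** (section 11.0 Statistical Considerations)

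The summaries and the proportion with AEs cover all four rows, in every treated patient. Rows one to three can be built from the CRF plus eSAE. Row four cannot.

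**Step 3. Effect on the proportion of patients with AEs**

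Inputs: up to 39 patients per cohort and 78 in total, and 19 in stage 1 (section 11.0 Statistical Considerations). It is assumed that every enrolled patient receives study drug and that the tables use CRF plus eSAE. A patient whose only AEs fall in row four is then counted as AE-free, which lowers the proportion by 1/N:

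- full cohort: 1/39 = 2.6 percentage points
- cohort stopped at stage 1: 1/19 = 5.3 points
- both full cohorts pooled: 1/78 = 1.3 points

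With k such patients the understatement is k/N. The documents give no basis for estimating k.

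**Step 4. Effect on the category tables**

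These are more exposed. A row-four event is missing from its category even when the patient has other AEs that are captured, so the same 1/N applies to more patients.

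For scale only, take the pooled levocarnitine percentages in Appendix I and assume that every such event is expected and non-serious:

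| Event | Appendix I | Of 39 | Of 78 |
|---|---|---|---|
| Diarrhea | 16% | 0.16 × 39 = 6.2 | 0.16 × 78 = 12.5 |
| Vomiting | 15% | 0.15 × 39 = 5.9 | 0.15 × 78 = 11.7 |
| Nausea | 8% | 0.08 × 39 = 3.1 | 0.08 × 78 = 6.2 |

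On those assumptions, none of these patients' events would appear in the table. Appendix I covers other doses and counts events regardless of causality, so these are not predictions.

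**Step 5. Patients whose records would need abstraction**

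- both cohorts stop at stage 1: 19 + 19 = 38
- one stops: 19 + 39 = 58
- neither stops: 39 + 39 = 78

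**The case against.** The strongest reply is that the plan contains no outright contradiction. The statistical section never says that the tables come from the CRF. All AEs are collected whatever their expectedness, so nothing is lost, and an analyst who works from the Adverse Event Record gets the right answer. Appendix C, which is cited for recording rules and was not supplied, may define expected events and name the data source.

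Much of this stands. The gap is recoverable, it vanishes if the full record is used, and its size is unknown. But the CRF is the only study database the protocol names, and its restriction carries no qualification. Following that rule and tabulating the database would understate a planned result. If Appendix C says otherwise, the two texts still have to be aligned.

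A second reply is that the restriction looks deliberate, to avoid transcribing the many background events seen during leukemia treatment, and that the burden follows the number of events more than the number of patients. This is fair. The AE definition covers unrelated events, and section 6.0 keeps patients on study until 30 days after the last dose of PEG-asparaginase or inotuzumab, so event counts could be large. It is a reason to choose an economical way of getting the data, but the planned tables still need the missing events.

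**Conclusion.** The point holds. As specified, the study database omits non-serious expected AEs, while the planned safety summaries include them. Tables built from the CRF plus eSAE would understate the proportion of patients with AEs by 2.6 points (N = 39), 5.3 points (N = 19) or 1.3 points (N = 78) for each patient whose only events are of that kind. They would also understate category frequencies for a wider group of patients. Tables built from the Adverse Event Record would have no such understatement.

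The conclusion rests on the supplied text alone: Appendix C was not available, and no supplied passage defines expected events or names the source of the safety tables. Confidence is medium for those reasons. The point concerns a descriptive secondary endpoint and should be corrected before the tables are built.

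**What to change.** 1. Check Appendix C. If it already provides for all AEs to reach the analysis, cite the relevant part and bring section 11.0 Reporting Requirements into line with it.
2. Otherwise, replace the restriction to unexpected events. Every AE on the Adverse Event Record, with grade and attribution, should either be entered in the CRF or be abstracted into a safety dataset. An expectedness flag would preserve the distinction the current rule makes.
3. State in section 11.0 Statistical Considerations that the safety tables use that dataset, reconciled with the serious-event reports.

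The cost is low: one or two sentences of text, plus transcription or abstraction of records that already exist for 38 to 78 patients. The main downside is the added entry of background leukemia events, and that work grows with the number of events. Sample size, type I error and power do not change.

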Appendix I

Adverse Events with a Frequency $\geq 5\%$ Regardless of Causality by Body System

| | Placebo (n=63) | Levcarnitine 10 mg (n=34) | Levcarnitine 20 mg (n=62) | Levcarnitine 40 mg (n=34) | Levcarnitine 10, 20 & 40 mg (n=130) |
|----------------------------|-------------------|------------------------------|------------------------------|------------------------------|---|
| Body as Whole | | | | | |
| Abdominal pain | 17 | 21 | 5 | 6 | 9 |
| Accidental injury | 10 | 12 | 8 | 12 | 10 |
| Allergic reaction | 5 | 6 | | | 2 |
| Asthenia | 8 | 9 | 8 | 12 | 9 |
| Back pain | 10 | 9 | 8 | 6 | 8 |
| Chest pain | 14 | 6 | 15 | 12 | 12 |
| Fever | 5 | 6 | 5 | 12 | 7 |
| Flu syndrome | 40 | 15 | 27 | 29 | 25 |
| Headache | 16 | 12 | 37 | 3 | 22 |
| Infection | 17 | 15 | 10 | 24 | 15 |
| Injection site reaction | 59 | 38 | 27 | 38 | 33 |
| Pain | 49 | 21 | 32 | 35 | 30 |
| Cardiovascular | | | | | |
| Arrhythmia | 5 | 3 | | 3 | 2 |
| Atrial fibrillation | | | 2 | 6 | 2 |
| Cardiovascular disorder | 6 | 3 | 5 | 6 | 5 |
| Electrocardiogram abnormal | | 3 | | 6 | 2 |
| Hemorrhage | 6 | 9 | 2 | 3 | 4 |
| Hypertension | 14 | 18 | 21 | 21 | 20 |
| Hypotension | 19 | 15 | 19 | 3 | 14 |
| Palpitations | | 3 | 8 | | 5 |
| Tachycardia | 5 | 6 | 5 | 9 | 6 |
| Vascular disorder | 2 | | 2 | 6 | 2 |
| Digestive | | | | | |
| Anorexia | 3 | 3 | 5 | 6 | 5 |
| Constipation | 6 | 3 | 3 | 3 | 3 |
| Diarrhea | 19 | 9 | 10 | 35 | 16 |
| Dyspepsia | 10 | 9 | 6 | | 5 |
| Gastrointestinal disorder | 2 | 3 | | 6 | 2 |
| Melena | 3 | 6 | | | 2 |
| Nausea | 10 | 9 | 5 | 12 | 8 |
| Stomach atony | 5 | | | | |
| Vomiting | 16 | 9 | 16 | 21 | 15 |
| Endocrine System | | | | | |
| Parathyroid disorder | 2 | 6 | 2 | 6 | 4 |
| Hemic/Lymphatic | | | | | |

| | | | | | |
|-----------------------|----|----|----|----|----|
| Anemia | 3 | 3 | 5 | 12 | 6 |
| Metabolic/Nutritional | | | | | |
| Hypercalcemia | 3 | 15 | 8 | 6 | 9 |
| Hyperkalemia | 6 | 6 | 6 | 6 | 6 |
| Hypervolemia | 17 | 3 | 3 | 12 | 5 |
| Peripheral edema | 3 | 6 | 5 | 3 | 5 |
| Weight decrease | 3 | 3 | 8 | 3 | 5 |
| Weight increase | 2 | 3 | | 6 | 2 |
| Musculo-Skeletal | | | | | |
| Leg cramps | 13 | | 8 | | 4 |
| Myalgia | 6 | | | | |
| Nervous | | | | | |
| Anxiety | 5 | | 2 | | 1 |
| Depression | 3 | 6 | 5 | 6 | 5 |
| Dizziness | 11 | 18 | 10 | 15 | 13 |
| Drug dependence | 2 | 6 | | | 2 |
| Hypertonia | 5 | 3 | | | 1 |
| Insomnia | 6 | 3 | 6 | | 4 |
| Paresthesia | 3 | 3 | 3 | 12 | 5 |
| Vertigo | | 6 | | | 2 |
| Respiratory | | | | | |
| Bronchitis | | | 5 | 3 | 3 |
| Cough increase | 16 | | 10 | 18 | 9 |
| Dyspnea | 19 | 3 | 11 | 3 | 7 |
| Pharyngitis | 33 | 24 | 27 | 15 | 23 |
| Respiratory disorder | 5 | | | | |
| Rhinitis | 10 | 6 | 11 | 6 | 9 |
| Sinusitis | 5 | | 2 | 3 | 2 |
| Skin And Appendages | | | | | |
| Pruritus | 13 | | 8 | 3 | 5 |
| Rash | 3 | | 5 | 3 | 3 |
| Special Senses | | | | | |
| Amblyopia | 2 | | 6 | | 3 |
| Eye disorder | 3 | 6 | 3 | | 3 |
| Taste perversion | | | 2 | 9 | 3 |
| Urogenital | | | | | |
| Urinary tract infect | 6 | 3 | 3 | | 2 |
| Kidney failure | 5 | 6 | 6 | 6 | 6 |
